4.2.3.3 Pharmacokinetic Endpoints

Serum samples will be obtained to measure PK of MK-8353 when given in combination with pembrolizumab. MK-8353 (Parts 1 and 2) and pembrolizumab (Part 1 only) serum peak and trough concentrations at planned visits and times will be summarized. Pharmacokinetic data of MK-8353 and pembrolizumab will be compared with the previously validated population PK model and potentially used to update the model.

4.2.3.4 Antidrug Antibody Assay

Formation of antidrug antibodies can potentially confound drug exposures at therapeutic doses, and prime for subsequent infusion-related toxicity. Antidrug antibody response to pembrolizumab at the beginning of each cycle will be determined to understand drug metabolism, exposure, and safety. Blood samples collected for antidrug antibody may only be stored at this time. Further analyses may be performed if required. If ongoing antidrug antibody sampling is deemed to be unnecessary by the Sponsor, it may be reduced or discontinued.

4.2.3.5 Tumor Markers

Serum samples will be obtained prior to study start and on Day 1 of each cycle to evaluate the kinetics of tumor markers such as CEA, CA-125, and CA 19-9, as appropriate. In a previous study, CEA decrease was predictive of PFS and ORR and occurred well in advance of radiographic confirmation of disease control [55]. Subjects with disease progression had rapid tumor marker elevation within 30 days after the initiation of therapy that significantly preceded radiographic changes [55].

4.2.3.6 RAS/RAF Mutations and pMMR/dMMR (MSI) Status

Testing for BRAF mutation (methodology detecting both V600E and/or V600K mutations), KRAS codon 12 and 13 mutations, and NRAS mutations (for non-CRC solid tumors) will be indicated according to tumor type as judged by the investigator, and performed by local laboratory testing.

Microsatellite instability, a form of genomic instability, occurs through the insertion or deletion of repeating nucleotides during deoxyribonucleic acid (DNA) replication and failure of the MMR system to correct errors in nucleotide repeat markers. Testing for pMMR/dMMR (MSI) status is already standardized and performed in Clinical Laboratory Improvement Amendments (CLIA)-certified laboratories without need for assay development. Mismatch repair proteins, or MSI loci testing for CRC is already clinically indicated as per National Comprehensive Cancer Network, European Society for Medical Oncology, and American Society of Clinical Oncology (ASCO) guidelines [58] [59] [60]. All means of testing for MSI status (eg, immunohistochemistry [IHC], polymerase chain reaction [PCR], next generation sequencing [NGS]) performed locally will be accepted. For other non-CRCs for which MSI testing is not currently clinically indicated, MSI status will be performed locally by CLIA-certified IHC or PCR-based tests for eligibility, or by a central laboratory if local laboratory testing is not available.

For central laboratory testing for MSI status, archived tumor samples or newly obtained biopsies will be used.

4.2.3.7 Planned Exploratory Biomarker Research

Planned Genetic Analysis

Additional biomarker research to identify factors important for MK-8353 and pembrolizumab combination therapy will be pursued.

Pretreatment and on-treatment tumor (when obtained) and blood samples collected in this study may undergo proteomic, genomic, and transcriptional analyses (both DNA and ribonucleic acid [RNA] analyses). Additional research may evaluate factors important for predicting responsiveness or resistance to MK-8353 and pembrolizumab combination therapy and other immunologic targets. Expression of candidate biomarkers in tumor tissue will be evaluated both at baseline and at least 10 to 14 days after initiation of combination therapy with MK-8353 and pembrolizumab (optional on-treatment biopsy in Cycle 2), including immune-signaling markers on the surface of tumor cells, phenotypic and functional immune cell markers on tumor-infiltrating lymphocytes (which may include PD-1, PD-L1, CD8 T cells), inhibition of ERK phosphorylation, and possible other biomarkers, as well as DNA/RNA changes. These and other additional biomarker or genomic research to identify factors important for MK-8353 and pembrolizumab combination therapy (eg, human leukocyte antigen genotype) may also be pursued.

Cancer immunotherapies represent an important and novel class of antitumor agents. However, the mechanism of action of these exciting new therapies is not completely understood and much remains to be learned regarding how best to leverage these new drugs in treating subjects. Thus, to aid future subjects, it is important to investigate the determinants of response or resistance to cancer immunotherapy as well as determinants of AEs in the course of clinical trials. These efforts will identify novel predictive/PD biomarkers and generate information that will better guide single-agent and combination therapy with immuno-oncology drugs. To identify novel biomarkers, we will collect biospecimens (eg, blood components, tumor material) to support analyses of cellular components (eg, protein, DNA, RNA, metabolites) and other circulating molecules. Investigations may include but are not limited to:

- Germline (blood) genetic analyses (eg, single nucleotide polymorphism analyses, whole exome sequencing, whole genome sequencing): this research will evaluate whether genetic variation within a clinical trial population correlates with response to the treatment(s) under evaluation. If genetic variation is found to predict efficacy or AEs, the data might inform optimal use of therapies in the subject population. Furthermore, it is important to evaluate germline DNA variation across the genome in order to interpret tumor-specific DNA mutations. Finally, MSI will be evaluated as this is an important biomarker for some cancers (ie, CRC).
- Genetic (DNA) analyses from tumor: the application of new technologies, such as next generation sequencing, has provided scientists the opportunity to identify tumor-specific DNA changes (eg, mutations, methylation status, MSI). Key molecular changes of interest to immuno-oncology drug development include the mutational burden of tumors and the clonality of T-cells in the tumor microenvironment. Increased mutational burden (sometimes referred to as a 'hyper-mutated' state) may generate neo-antigen presentation in the tumor

microenvironment. To conduct this type of research, it is important to identify tumor-specific mutations that occur across all genes in the tumor genome. Thus, genome-wide approaches may be used for this effort. Note that in order to understand tumor-specific mutations; it is necessary to compare the tumor genome with the germline genome. Microsatellite instability will also be evaluated as this is an important biomarker for some cancers (ie, CRC).

- Tumor and blood RNA analyses: both genome-wide and targeted messenger RNA expression profiling and sequencing in tumor tissue and in blood may be performed to define gene signatures that correlate to clinical response to treatment with pembrolizumab or other immunotherapies. Pembrolizumab induces a response in tumors that likely reflects an inflamed/ immune phenotype. Specific immune-related gene sets (such as those capturing interferon-gamma transcriptional pathways) may be evaluated and new signatures may be identified. Individual genes related to the immune system may also be evaluated (eg, interleukin-10). MicroRNA profiling may also be pursued.
- Proteomics and IHC using blood or tumor: tumor and blood samples from this study may undergo proteomic analyses (eg, PD-L1 IHC). PD-L1 protein level in tumor sections, assessed by IHC, has been shown to correlate with response to pembrolizumab in subjects with NSCLC, and an in vitro diagnostic device has been developed for use with pembrolizumab in NSCLC. Preliminary data indicate that this association may also be true in additional cancer types (ie, triple-negative breast cancer, head and neck cancer, and gastric cancer). Additional tumor or blood-derived proteins may also correlate with response to pembrolizumab. Tumor tissue may, therefore, be subjected to proteomic analyses using a variety of platforms that could include, but are not limited to, immunoassays and liquid chromatography/mass spectrometry. This approach could identify novel protein biomarkers that could aid in subject selection for pembrolizumab therapy.
- Other blood-derived biomarkers: in addition to expression on tumor tissue, PD-L1 and other tumor-derived proteins can be shed from tumors and released into the blood. Assays such as enzyme-linked immunoassay measure these proteins in serum. Correlation of expression with response to pembrolizumab therapy may identify new approaches for predictive biomarkers in blood, representing a major advance from today's reliance on assessing tumor biomarkers. This research would serve to develop such assays for future clinical use.

4.2.3.8 Future Biomedical Research

The Sponsor will conduct Future Biomedical Research (FBR) on specimens consented for FBR during this clinical trial. This research may include genetic analyses (DNA), gene expression profiling (RNA), proteomics, metabolomics (serum, plasma) and/or the measurement of other analytes, depending on which specimens are consented for future biomedical research.

Such research is for biomarker testing to address emergent questions not described elsewhere in the protocol (as part of the main trial) and will only be conducted on specimens from appropriately consented subjects. The objective of collecting specimens for FBR is to

explore and identify biomarkers that inform the scientific understanding of diseases and/or their therapeutic treatments. The overarching goal is to use such information to develop safer, more effective drugs/vaccines, and/or to ensure that subjects receive the correct dose of the correct drug/vaccine at the correct time. The details of FBR are presented in Section 12.2. Additional informational material for institutional review boards/ethics review committees (IRBs/ERCs) and investigational site staff is provided in Section 12.1.

4.3 Benefit/Risk

Subjects in clinical trials generally cannot expect to receive direct benefit from treatment/vaccination during participation, as clinical trials are designed to provide information about the safety and effectiveness of an investigational medicine.

Additional details regarding specific benefits and risks for subjects participating in this clinical trial may be found in the accompanying MK-8353 and pembrolizumab IB and informed consent documents.

5 METHODOLOGY

5.1 Entry Criteria

5.1.1 Diagnosis/Condition for Entry into the Trial

Male/Female subjects with advanced or metastatic solid tumors in Part 1 and Male/Female subjects with \geq second line advanced or metastatic non-MSI-H/dMMR CRC in Part 2 will be enrolled in this trial.

5.1.2 Subject Inclusion Criteria

In order to be eligible for participation in this trial, the subject must:

1. Part 1: have a histologically or cytologically documented, locally advanced or metastatic solid malignancy. Each subject must have received at least 1 and up to 5 prior lines of cancer treatment regimen, excluding neo-adjuvant, adjuvant, maintenance treatment and surgery.

Note: a repeat line of treatment does not count in the total number if the subject did not progress the first time; a 2-week or more duration of treatment counts in the total number of prior line of treatment if the subject progressed.

2. Part 2: have a histologically confirmed adenocarcinoma originating from the colon or rectum (Stage 4 American Joint Committee on Cancer 7th edition). Must be non-MSI-H/dMMR CRC. Appendiceal cancer is included.

AND

Experienced disease progression or was intolerant to at least 1 and up to 5 systemic chemotherapy regimen for metastatic non-MSI-H/dMMR CRC that must have included fluoropyrimidines **and** irinotecan, or oxaliplatin, \pm anti-vascular endothelial growth factor or anti-epidermal growth factor receptor (if indicated by RAS mutational status); disease progression must have occurred within 3 months of the last systemic therapy administration. Subjects who were not deemed appropriate candidate for any of these agents due to medical history and/or contraindications may be eligible upon consultation with the Sponsor.

3. Provide an archival or newly obtained tumor tissue sample and blood samples for assessment of RAS/RAF mutation and pMMR/dMMR status and for biomarker analysis.
4. Have at least 1 measurable lesion as defined by RECIST 1.1 on imaging studies (CT or MRI) as assessed by the investigator/local radiology review. Cutaneous lesions and other superficial lesions that are detectable only by physical examination and subcutaneous lesions detectable by CT are not considered measurable lesions for the purposes of this protocol, but may be considered as nontarget lesions.
5. Be willing and able to provide written informed consent for the trial. The subject may also provide consent for FBR. However, the subject may participate in the main trial without participating in FBR.
6. Be ≥ 18 years of age on day of signing the informed consent.
7. Have a performance status of 0 or 1 on the ECOG Performance Scale.
8. Have an anticipated life expectancy of at least 3 months.
9. Be able to swallow and retain oral medication and must not have any clinically significant gastrointestinal abnormalities that may alter absorption.
10. Have adequate organ function as defined in [Table 1](#):

Table 1 Inclusion Criteria Laboratory Parameters

System	Laboratory Value
Hematological	
ANC	$\geq 1,500/\text{mcL}$
Platelets	$\geq 100,000/\text{mcL}$
Hemoglobin	$\geq 9 \text{ g/dL}$ or $\geq 5.6 \text{ mmol/L}$
Renal	
Serum creatinine OR Measured or calculated ^a CrCl (GFR can also be used in place of creatinine or CrCl)	$\leq 1.5 \times \text{ULN}$ OR $\geq 60 \text{ mL/min}$ for subject with creatinine levels $>1.5 \times$ institutional ULN
Hepatic	
Serum total bilirubin	$\leq 1.5 \times \text{ULN}$ OR Direct bilirubin $\leq \text{ULN}$ for subjects with total bilirubin levels $>1.5 \times \text{ULN}$
AST (SGOT) and ALT (SGPT)	$\leq 2.5 \times \text{ULN}$ OR $\leq 5 \times \text{ULN}$ for subjects with liver metastases
Coagulation	
INR or PT aPTT	$\leq 1.5 \times \text{ULN}$ unless the subject is receiving anticoagulant therapy as long as PT or aPTT is within therapeutic range of intended use of anticoagulants

^a Calculate CrCl using standard Cockcroft-Gault formula (Appendix 12.3).
 ALT (SGOT)=alanine aminotransferase; ANC=absolute neutrophil count; aPTT=activated partial thromboplastin time; AST (SGPT)=aspartate aminotransferase; CrCl=creatinine clearance; GFR=glomerular filtration rate; INR=International Normalized Ratio; PT=prothrombin time; ULN=upper limit of normal.

11. Female subject of childbearing potential must have a negative urine or serum pregnancy test within 72 hours prior to receiving the first dose of study medication. If the urine test is positive or cannot be confirmed as negative, a serum pregnancy test will be required. The serum pregnancy test must be negative for the subject to be eligible.

12. Female subjects may be enrolled in the trial if they are:

- Of nonchildbearing potential, which is defined as:
 - A female subject ≥ 45 years of age and has not had menses for greater than 1 year,
 - A female who is amenorrheic for >2 years without a hysterectomy and oophorectomy and a follicle-stimulating hormone (FSH) value in the postmenopausal range upon pretrial (screening) evaluation,
and/or
 - A female who is status post hysterectomy, oophorectomy, or tubal ligation. Documented hysterectomy or oophorectomy must be confirmed with medical records of the actual procedure or confirmed by an ultrasound. Tubal ligation must be confirmed with medical records of the actual procedure; otherwise, the subject will be excluded. Information must be captured appropriately within the site's source documents.
- Of childbearing potential who are willing to use either 2 adequate barrier methods, or to abstain from heterosexual activity throughout the trial, starting with the screening visit (Visit 1) through 120 days after the last dose of trial treatment. Please refer to Section 5.7.2 for a list of acceptable birth control methods.

13. Male subjects of childbearing potential must agree to use an adequate method of contraception as outlined in Section 5.7.2, starting with the first dose of study medication through 120 days after the last dose of study medication.

Note: Abstinence is acceptable if this is the usual lifestyle and preferred contraception.

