5.7.2 Contraception

MK-8353 and/or pembrolizumab may have adverse effects on a fetus in utero. Furthermore, it is not known if MK-8353 and/or pembrolizumab have transient adverse effects on the composition of sperm.

For this trial, male subjects will be considered to be of nonreproductive potential if they have azoospermia (whether due to having had a vasectomy or due to an underlying medical condition).

Female subjects will be considered of nonreproductive potential if they are either:

- (1) Postmenopausal (defined as at least 12 months with no menses without an alternative medical cause; in women <45 years of age a high FSH level in the postmenopausal range may be used to confirm a postmenopausal state in women not using hormonal contraception or hormonal replacement therapy. In the absence of 12 months of amenorrhea, a single FSH measurement is insufficient.);

OR

- (2) Have had a hysterectomy and/or bilateral oophorectomy, bilateral salpingectomy, or bilateral tubal ligation/occlusion, at least 6 weeks prior to screening;

OR

- (3) Has a congenital or acquired condition that prevents childbearing.

Female and male subjects of reproductive potential must agree to avoid becoming pregnant or impregnating a partner, respectively, while receiving MK-8353 and/or pembrolizumab and for 120 days after the last dose. Subjects must comply with one of the following:

- (1) Practice abstinence[†] from heterosexual activity;

OR

- (2) Use (or have their partner use) acceptable contraception during heterosexual activity.

Acceptable methods of contraception are[‡]:

Single method (one of the following is acceptable):

- Intrauterine device
- Vasectomy of a female subject's male partner
- Contraceptive rod implanted into the skin

Combination method (requires use of 2 of the following):

- Diaphragm with spermicide (cannot be used in conjunction with cervical cap/spermicide)

- Cervical cap with spermicide (nulliparous women only)
- Contraceptive sponge (nulliparous women only)
- Male condom or female condom (cannot be used together)
- Hormonal contraceptive: oral contraceptive pill (estrogen/progestin pill or progestin-only pill), contraceptive skin patch, vaginal contraceptive ring, or subcutaneous contraceptive injection

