7.1.3.1 Laboratory Safety Evaluations (Hematology, Chemistry and Urinalysis)

Laboratory tests for hematology, chemistry and urinalysis are specified in [Table 9](#).

Table 9 Laboratory Tests

Hematology	Chemistry	Urinalysis	Other
Red blood cell (RBC) count	Total protein	Blood	Prothrombin time (PT)/International normalized ratio (INR) ⁴
Hemoglobin	Albumin	Glucose	Activated partial thromboplastin time (aPTT) ⁴
Hematocrit	Alanine aminotransferase (ALT)	Protein	Thyroid function testing (T4, T3, TSH) ⁵
White blood cell (WBC) count (total and differential)	Aspartate aminotransferase (AST)	Specific gravity	Serum β-human chorionic gonadotropin (β-hCG) ³
Absolute neutrophil count (ANC)	Alkaline phosphatase	Microscopic exam, if abnormal results are noted	Follicle stimulating hormone (FSH) ⁶
Platelet count	Lactate dehydrogenase (LDH)	Urine pregnancy test ³	Human immunodeficiency virus (HIV; HIV Type 1 and Type 2)
	Gamma glutamyl transferase (GGT)		Hepatitis (HCV, RNA [qualitative], or Hepatitis C antibody, and HBsAg)
	Total bilirubin		
	Direct bilirubin, if total bilirubin is above the upper limit of normal		
	Bicarbonate/Carbon dioxide (CO ₂) ¹		
	Calcium		
	Chloride		
	Phosphorus		
	Potassium		
	Sodium		
	Glucose		
	Creatinine		
	Cystatin C		
	Blood urea nitrogen (BUN)/Urea ²		
	Uric acid		

Hematology	Chemistry	Urinalysis	Other
	Amylase		
	Lipase		

1. If bicarbonate/CO₂ testing is not done as part of standard of care in your region then these tests do not need to be performed.

2. Blood urea nitrogen is preferred; if not available urea may be tested.

3. Women of childbearing potential only. Urine pregnancy test is preferred. If the urine test is positive or cannot be confirmed as negative, a serum pregnancy test is required.

4. Coagulation factors (PT/INR and aPTT) should be tested as part of the screening procedures for all subjects. Any subject receiving anticoagulant therapy should have coagulation factors monitored closely throughout the trial.

5. Total T3 is preferred; if not available free T3 may be tested. Total T4 is preferred; if not available free T4 may be tested.

6. In women <45 years of age, a high FSH level in the postmenopausal range may be used to confirm a postmenopausal state in women not using hormonal contraception or hormone replacement therapy. In the absence of 12 months of amenorrhea, a single FSH measurement is insufficient.

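### Inclusion criterion 12 and Section 5.7.2 define nonchildbearing potential differently, and the protocol does not say which definition governs

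*Combined protocol and SAP*

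**What the plan says.** Criterion 12 (Section 5.1.2) gives three routes to nonchildbearing potential:

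- a woman of 45 or older who "has not had menses for greater than 1 year";
- "A female who is amenorrheic for >2 years without a hysterectomy and oophorectomy", with a postmenopausal FSH value at screening;
- "A female who is status post hysterectomy, oophorectomy, or tubal ligation", subject to documentation of the procedure.

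Section 5.7.2 gives three different routes to nonreproductive potential:

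- postmenopausal, "defined as at least 12 months with no menses without an alternative medical cause", where in women under 45 FSH may confirm the state only if they are not on hormonal contraception or replacement therapy;
- "Have had a hysterectomy and/or bilateral oophorectomy, bilateral salpingectomy, or bilateral tubal ligation/occlusion, at least 6 weeks prior to screening";
- a congenital or acquired condition that prevents childbearing.

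Table 9 note 6 (Section 7.1.3.1) follows the second text: "a high FSH level in the postmenopausal range may be used to confirm a postmenopausal state", again only off hormones.

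Criterion 12 refers to Section 5.7.2 for birth control methods, not for the definition.

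**The concern.** Both definitions decide the same two things: who is tested for pregnancy before the first dose, and who must use contraception. The protocol itself gives the reason for care: "MK-8353 and/or pembrolizumab may have adverse effects on a fetus in utero".

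The terms do not settle which definition applies. Criterion 11 (the pregnancy test), Table 9 note 3 and the closing paragraph of Section 5.7.2 speak of *childbearing potential*, which is criterion 12's term. The definitions and the main obligation in Section 5.7.2, and note 20 of both flow charts, speak of *reproductive potential*. Section 7.1.1.2 sends the eligibility review to Sections 5.1.2 and 5.1.3 only. A careful site could therefore apply criterion 12's definition to both the test and contraception.

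Later checks would not reliably correct an error at entry. After the first dose, note 20 asks for monthly testing only where local regulations call for it. Exclusion 19 bars women who are pregnant or expecting to conceive, but prescribes neither a test nor contraception.

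**Working it through.** No figure in the plan depends on this point, so the check sets the two definitions side by side. Each profile assumes that no other route applies to the woman.

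| Profile | Criterion 12 | Section 5.7.2 |
|---|---|---|
| Tubal ligation less than 6 weeks before screening | Nonchildbearing | Reproductive |
| Hysterectomy or bilateral oophorectomy less than 6 weeks before screening | Nonchildbearing | Fails the surgical route; the third route is arguable |
| Age 45 or over, more than 1 year of amenorrhea, alternative medical cause | Nonchildbearing | Reproductive |
| Any age, more than 2 years of amenorrhea, postmenopausal FSH, alternative medical cause | Nonchildbearing | Reproductive |
| Under 45, more than 2 years of amenorrhea, postmenopausal FSH measured on hormones | Nonchildbearing | FSH cannot confirm; not clearly postmenopausal |
| Unilateral oophorectomy | Nonchildbearing if read literally | Reproductive |
| Under 45, 12 to 24 months of amenorrhea, no other cause | Childbearing | Nonreproductive; FSH may be used to confirm |
| Bilateral salpingectomy | Not listed | Nonreproductive |
| Condition that prevents childbearing | Not listed | Nonreproductive |

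The first six rows are less protective under criterion 12. They come from four conditions that only Section 5.7.2 contains: bilateral surgery, 6 weeks (42 days) since surgery, no alternative medical cause, and no hormones when FSH is used. The last three rows are stricter under criterion 12.

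**Duration if criterion 12 alone were used.** Section 2.1 allows 35 cycles in Arms A, B and C, and 36 in Arm D, where Cycle 1 is a 14-day run-in. A cycle is otherwise 21 days (Section 5.2). Contraception runs to 120 days after the last dose.

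- Arms A, B and C: 35 × 21 = 735; 735 + 120 = 855 days.
- Arm D: 14 + 35 × 21 = 749; 749 + 120 = 869 days.

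These are nominal figures for uninterrupted treatment. Dose delays (Section 5.2.2.1) and re-treatment after complete response (Section 5.8.1.1) can lengthen the period. Criterion 12's contraception period also starts at screening, up to 28 days before Cycle 1 Day 1. Progression or toxicity will shorten it for many women. For recent surgery the practical gap is much shorter if the 6 weeks is read as a waiting time, because it closes once that interval has passed.

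**The case against.** The strongest reply is that the texts can be followed together. A site enrols under criterion 12 and then applies Section 5.7.2, which states: "Female and male subjects of reproductive potential must agree to avoid becoming pregnant or impregnating a partner, respectively". Note 20 ties a test, at screening and within 72 hours before the first dose, to reproductive potential, a term defined only in Section 5.7.2. That section also makes its contraception requirement a condition of taking part. Exclusion 19 and immediate discontinuation on pregnancy (Section 5.7.3) add protection. This stands: a site that applies all of these leaves no gap. What it does not remove is the other reading, because criterion 11, Table 9 note 3 and the closing paragraph of Section 5.7.2 use criterion 12's term.

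Some of the groups are also thin. An investigator may well take oophorectomy, given as a reason for nonchildbearing potential, to mean bilateral. A recent hysterectomy or bilateral oophorectomy may fit Section 5.7.2's third route, which leaves recent tubal ligation as the clear surgical case. Amenorrhea with an alternative medical cause is the most solid group, but its size is unknown.

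Three stronger readings are tempting, and the documents support none of them:

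- A reader might infer that the protocol leaves these women without a test or contraception. It does so only where a site uses criterion 12's definition throughout.
- A reader might take 855 or 869 days as the longest possible gap. Delays, re-treatment and the screening start can all extend it.
- A reader might conclude that criterion 12 is simply the stricter text below 45, and that its rule of more than 2 years plus FSH should replace Section 5.7.2's. That bullet states no age limit, and it lacks both the alternative-cause and the hormone-use conditions. Moving it across as it stands could weaken Section 5.7.2.

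**Conclusion.** The conflict is real and holds on the text. Two definitions of the same status sit in one protocol without a rule of precedence, and criterion 12 is the less protective on surgery timing, cause of amenorrhea, hormone use with FSH and, read literally, laterality. It is the stricter one for women under 45 with 12 to 24 months of amenorrhea, for bilateral salpingectomy and for conditions that prevent childbearing.

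The consequence depends on site practice. It arises only if a site applies criterion 12's definition to both the test and contraception. The documents give no basis for estimating how many women that would involve. The durations above describe nominal, uninterrupted treatment. No estimate, sample size or analysis population changes. The point is one of subject safety and clear wording; it merits correction because the potential harm is fetal exposure and the remedy is cheap.

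**What to change.** 1. Replace criterion 12's definition with a reference to the single definition in Section 5.7.2. That definition should state: hysterectomy, or bilateral oophorectomy, salpingectomy or tubal ligation/occlusion, at least 6 weeks before screening; amenorrhea without an alternative medical cause; FSH used only in women not on hormonal contraception or replacement therapy; or a congenital or acquired condition that prevents childbearing.
2. Keep criterion 12's documentation rules: records or ultrasound for hysterectomy and oophorectomy, records for tubal ligation. The ligation rule can be extended to salpingectomy.
3. Use one term, tied to that definition, in criteria 11 and 12, Table 9 note 3, note 20 of both flow charts and all of Section 5.7.2.
4. Do not carry the rule of more than 2 years plus FSH into Section 5.7.2 unless both safeguards go with it.

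Optionally, align criterion 12's two barrier methods or abstinence with the methods listed in Section 5.7.2, some of which are accepted singly. The present mismatch errs on the strict side.

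The cost is wording, plus a urine test and contraception for a few more women. The three profiles for which criterion 12 is now stricter would be classed as Section 5.7.2 already classes them. No new type of procedure, visit or analysis is needed.
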